--	---

Trial objectives:	
Primary Objective
 
To assess safety and tolerability of apaglutide in subjects with SR lower GI-aGVHD Grade II to IV Mount Sinai aGVHD International Consortium (MAGIC) who are treated with SS and RUX
 
Secondary Objectives
 
To evaluate the overall response rate (partial response [PR] and complete response [CR]) at Day 56, on the lower GI tract MAGIC score, in subjects with SR lower GI-aGVHD Grade II to IV MAGIC that are treated with apaglutide, SS, and RUX compared to SS and RUX alone (BAT)
 
To evaluate the overall response rate (PR and CR) at Days 14, 28, 91, 119, 147, and 182 on the lower GI-tract MAGIC score
 
To evaluate the overall response rate (PR and CR) at Days 14, 28, 56, 91, 119, 147, and 182 on the total MAGIC score
 
To evaluate the rate of durable overall response rate from Day 28 to Day 56
 
To evaluate duration of response from Day 56 on the total MAGIC score
 
To assess the individual durations of lower GI response (according to the MAGIC score)
 
To assess the individual durations of lower GI response (according to the MAGIC score) in subjects that were re-treated with apaglutide because of a lower GI-aGVHD flare
 
To assess the time to partial lower GI-aGVHD response as defined by the MAGIC score
 
To assess the time to complete lower GI-aGVHD response as defined by the MAGIC score
 
To assess best overall response
 
Assessment of failure-free survival (FFS¹)
 
To assess NRM²

--------------------------	---

¹ The time from the date of randomization/Day 0 to the date of hematologic disease relapse/progression, non-relapse mortality, or addition of new systemic aGVHD treatment

² The time from date of randomization/Day 0 to the date of death not preceded by hematologic disease relapse/progression

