16.2 Appendix: Definitions of Terms

The following definitions (derived from Supplementary Appendix in Zeiser, 2020a) will apply in this trial:

Term	Definition
Graft failure	
Primary graft failure:
 
Absolute neutrophil count $<0.5 \times 10^9/L$ by Day 28 Hemoglobin $<80 \text{ g/L}$ and platelets $<20 \times 10^9/L$ Reduced intensity conditioning: Confirmation of donor cell origin is required Cord blood transplant: Up to Day +42
 
Secondary graft failure:
 
Absolute neutrophil count $<0.5 \times 10^9/L$ after initial engraftment not related to relapse, infection, or drug toxicity Reduced intensity conditioning: Loss of donor hematopoiesis to $<5\%$

Failure-free survival	The time from the date of randomization/Day 0 to the date of hematologic malignancy relapse/progression, non-relapse mortality, or addition of new systemic acute graft versus host disease (aGVHD) treatment
Non-relapse mortality	The time from date of randomization/Day 0 to date of death not preceded by hematologic malignancy relapse/progression
Overall survival	The time from the date of randomization/Day 0 to the date of death due to any cause
Malignancy relapse/progression	The time from date of randomization/Day 0 to hematologic malignancy relapse/progression
Complete response	A score of 0 for the aGVHD grading in all evaluable organs that indicates complete resolution of all signs and symptoms of aGVHD in all evaluable organs without administration of additional systemic therapies for any earlier progression, mixed response or non-response of aGVHD
Complete lower gastrointestinal (GI)-aGVHD response	The resolution of all lower GI-aGVHD signs and symptoms GVHD without administration of additional systemic therapies for any earlier progression, mixed response, or non-response of lower GI-aGVHD
Partial response	An improvement of one Stage in one or more organs involved with aGVHD signs or symptoms without progression in other organs or sites without administration of additional systemic therapies for an earlier progression, mixed response, or non-response of aGVHD
Partial lower GI-aGVHD response	An improvement of one Stage in the signs and symptoms of lower GI-aGVHD without administration of additional systemic therapies for any earlier progression, mixed response, or non-response of lower GI-aGVHD
Lack of response	Defined as stable disease, mixed response, or progression

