#### *4.3.9.14 Failure-free survival up to 2 years post-first dose of apraglutide*

The failure-free survival time is defined as the time from the date of the first dose to the date of hematologic malignancy relapse/progression, non-relapse mortality, or the start of additional systemic therapy for GI-aGVHD, whichever occurs first.

The failure-free survival will be summarized using Kaplan-Meier estimator. The number and percentage of subjects experiencing an event, and subjects censored will be summarized by apraglutide dose levels and in total. The median time-to-event will be presented where possible, along with the range and the associated two-sided 95% Brookmeyer-Crowley confidence interval. The event-free rate with 95% CI using Greenwood’s formula will be provided for selected time points (e.g., 1, 3, 6, 12 and 24 months).

Subject for which neither “new systemic therapy for aGVHD”, “hematologic malignancy relapse/progression” or “non-relapse mortality” event occurs will be right censored at their last follow-up visit.

Plots of the Kaplan-Meier estimate for the failure-free survival will be presented by apraglutide dose levels and in total.

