## APPENDIX A: DEFINITIONS OF TERMS

The following definitions will apply in this trial:

Term	Definition
Graft failure	
Primary graft failure:
 
Absolute neutrophil count <math><0.5 \times 10^9/L</math> by Day 28 Hemoglobin <math><80 \text{ g/L}</math> and platelets <math><20 \times 10^9/L</math> Reduced intensity conditioning: Confirmation of donor cell origin is required Cord blood transplant: Up to Day +42
 
Secondary graft failure:
 
Absolute neutrophil count <math><0.5 \times 10^9/L</math> after initial engraftment not related to relapse, infection, or drug toxicity Reduced intensity conditioning: Loss of donor hematopoiesis to <math><5\%</math>

Failure-free survival	The time from the date of randomization/Day 0 to the date of hematologic malignancy relapse/progression, non-relapse mortality, or addition of new systemic acute graft versus host disease (aGVHD) treatment
Non-relapse mortality	The time from date of randomization/Day 0 to date of death not preceded by hematologic malignancy relapse/progression
Overall survival	The time from the date of randomization/Day 0 to the date of death due to any cause
Malignancy relapse/progression	The time from date of randomization/Day 0 to hematologic malignancy relapse/progression
Complete response	A score of 0 for the aGVHD grading in all evaluable organs that indicates complete resolution of all signs and symptoms of aGVHD in all evaluable organs without administration of additional systemic therapies for any earlier progression, mixed response or non-response of aGVHD

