
“Additional systemic therapy” definition for the complete and partial response definition
	
Any GVHD systemic therapy being started after apaglutide initiation to achieve GVHD control, i.e. any medication or procedure marked as Reason for medication = “aGVHD treatment” and “Is this an additional, new systemic therapy for an earlier progression, mixed response or non-response of aGVHD?” = Yes in the CM or PR page of the eCRF.
 
Note:
 
 
- Increases or addition of a new systemic steroid will not be counted as new or additional GVHD therapy.
 
Budesonide and beclametasone not to be considered as new GVHD therapy
 
- Change in dose of CNIs will not be considered as additional GVHD therapy if already given prior to apaglutide
 
 
New CNIs after apaglutide initiation should be considered as a new systemic therapy, if marked as “aGVHD treatment” and “Is this an additional, new systemic therapy for an earlier progression, mixed response or non-response of aGVHD?”; these will not be considered as new therapy if marked as “prophylaxis for a drug side effect”.

Complete lower gastrointestinal (GI)-aGVHD response
	
The resolution of all lower GI-aGVHD signs and symptoms (score of 0 for aGVHD grading) of GVHD without administration of additional systemic therapies for any earlier progression, or non-response of lower GI-aGVHD.

Partial response
	
An improvement of one stage in one or more organs involved with aGVHD signs or symptoms without progression in other organs or sites without administration of additional systemic therapies for an earlier progression, mixed response, or non-response of aGVHD

Partial lower GI-aGVHD response
	
An improvement of one stage in the signs and symptoms of lower GI-aGVHD without administration of additional systemic therapies for any earlier progression or non-response of lower GI-aGVHD.

Lack of response	Defined as stable disease, mixed response, or progression
Stable disease	An absence of improvement in all organs involved by aGVHD, without worsening in all involved organs or development of signs or symptoms of aGVHD in a new organ
Stable disease (lower GI-aGVHD)	An absence of improvement or absence of worsening in lower GI-aGVHD
Mixed response	An improvement of at least 1 stage in the severity of aGVHD in one organ accompanied by progression in another organ or development of signs or symptoms of aGVHD in a new organ

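### The failure-free survival event in SAP 4.3.9.14 is limited to therapy for GI-aGVHD, which conflicts with its own censoring sentence, SAP Appendix A and the protocol

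*SAP*

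**What the plan says.** FFS is a secondary endpoint. In SAP 3.2 it carries no restriction to one analysis step, so under SAP Section 1 it is reported at both the Primary and the EOT analyses. Its therapy component is worded as follows.

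- SAP 4.3.9.14, definition sentence: failure is relapse/progression, non-relapse mortality, or "the start of additional systemic therapy for GI-aGVHD, whichever occurs first".
- SAP 4.3.9.14, censoring sentence: a subject is censored at the last follow-up visit if none of three events occurred, and the therapy event is named as "new systemic therapy for aGVHD".
- SAP Appendix A, FFS entry: "addition of new systemic acute graft versus host disease (aGVHD) treatment".
- Protocol synopsis, footnote 1: "non-relapse mortality, or addition of new systemic aGVHD treatment".
- Protocol Appendix 16.2: "non-relapse mortality, or addition of new systemic acute graft versus host disease (aGVHD) treatment".

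SAP Appendix A also has an entry for additional systemic therapy, labelled for the complete and partial response definitions. It covers "Any GVHD systemic therapy being started after apaglutide initiation to achieve GVHD control", identified from two eCRF items: the reason for medication, and whether the therapy is new and given for earlier progression, mixed response or non-response of aGVHD. It adds: "Increases or addition of a new systemic steroid will not be counted as new or additional GVHD therapy".

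SAP Section 6 lists 12 changes from the protocol. Item 4 says that wording on additional systemic therapies was added to Appendix A. No item mentions the FFS event.

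**The concern.** The definition sentence is the only one of the five statements with an organ restriction. Subjects are enrolled for lower GI disease, but the population is not GI-only. Skin, liver and upper GI are staged as well (protocol 5.5), response is reported by organ system, and inclusion criterion 6c covers progression to a new organ. New systemic therapy given for skin or liver disease is therefore possible.

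Section 4.3.9.14 has no consistent rule for such a subject, and two programmers could code the case differently. At stake are a time-to-event endpoint with an undefined event status, a possible departure from the protocol endpoint that is not declared, and a shift in one direction if the narrow sentence is followed. The protocol (7.8.2) also names FFS as an example for comparison with external data. A narrower event would make any later comparison of that kind unlike-for-unlike.

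**Working it through.** The documents give no FFS rate, event count or power for FFS, so there is no stated figure to reproduce. The check compares the texts and then works out the direction and the unit size.

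**1. The five statements side by side**

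| Place | Therapy that counts as failure | Organ limit |
|---|---|---|
| SAP 4.3.9.14, definition | additional systemic therapy | GI |
| SAP 4.3.9.14, censoring | new systemic therapy | none |
| SAP Appendix A, FFS entry | new systemic treatment | none |
| Protocol synopsis, footnote 1 | new systemic treatment | none |
| Protocol Appendix 16.2 | new systemic treatment | none |

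**2. A subject who starts new systemic therapy for skin or liver aGVHD only, with no relapse and no death**

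- Definition sentence: not an event, because the therapy is not for GI disease.
- Censoring sentence: not censorable, because new systemic therapy for aGVHD did occur.
- Appendix A and protocol: an event on the date the therapy was added.

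The section assigns this subject no status.

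**3. Direction**

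For each subject let

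- T_broad = earliest of relapse/progression, non-relapse mortality, any new systemic aGVHD therapy;
- T_narrow = earliest of relapse/progression, non-relapse mortality, new systemic therapy for GI-aGVHD.

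Therapy for GI-aGVHD is a subset of therapy for aGVHD, so T_narrow ≥ T_broad for every subject, and P(T_narrow > t) ≥ P(T_broad > t) at every t. Equality holds when no subject has non-GI therapy as first failure. This is a statement about the FFS times and the underlying curve. In a small sample with censoring, an event moved past other subjects' censoring times carries a larger Kaplan-Meier step, so the estimated difference need not follow the ordering at every time.

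**4. Size per subject, without censoring**

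Let k be the number of subjects whose only failure by time t is new systemic therapy for non-GI aGVHD. The narrow FFS(t) exceeds the broad FFS(t) by k/N. N is 15 per arm and 30 randomized (protocol 7.4), or up to 34 with the low body weight cohort.

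| k | N = 15 | N = 30 | N = 34 |
|---|---|---|---|
| 0 | 0 | 0 | 0 |
| 1 | 6.7 points | 3.3 points | 2.9 points |
| 2 | 13.3 points | 6.7 points | 5.9 points |
| 3 | 20.0 points | 10.0 points | 8.8 points |

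The documents do not give k. The range 0 to 3 is an assumption. A subject who also relapses, dies or starts GI therapy by t is already a failure under both readings and does not count towards k.

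**5. Illustration with assumed hazards**

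Assume independent exponential hazards: 0.8 per year for all other failures and h per year for non-GI-only therapy. One-year FFS is exp(-0.8) = 44.9% under the narrow reading and exp(-(0.8 + h)) under the broad one:

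- h = 0: 44.9%, no difference
- h = 0.05: 42.7%, difference 2.2 points
- h = 0.10: 40.7%, difference about 4.3 points
- h = 0.20: 36.8%, difference 8.1 points

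A simulation with 200,000 draws per setting gave the same values to within about 0.2 points. Neither hazard comes from the documents, so these figures show the shape of the effect and do not estimate it.

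**The case against.** The strongest reply is that no restriction was intended. The documents use GI-aGVHD loosely. SAP 4.3.9.10 and protocol Appendix 16.2 use additional therapy for GI-aGVHD as the cut-off for best overall response across all organs. SAP 4.3.9.7 says GI-aGVHD in its text, while its own Table 4-3 says aGVHD. SAP 4.3.9.2 makes a subject a non-responder for both lower GI and overall response after new systemic therapy, with no organ split. The eCRF items in Appendix A carry no organ either, so programming from them would capture the broad event and miss no failures. Every subject has lower GI-aGVHD by eligibility, so therapy for non-GI disease alone may never occur. FFS is also a descriptive Kaplan-Meier summary, with no external comparison planned for the Primary Analysis and no formal dose comparison (SAP Section 6, items 7 and 12).

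Most of this stands. It rules out the stronger reading that a reader might take from the definition sentence alone: that the SAP has chosen a GI-only event, so failures will be missed and FFS is overstated. The SAP contradicts itself and does not clearly adopt the narrow event. A fixed bias built from guessed therapy rates would have no source in the documents, and it must not exclude zero.

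The reply does not remove the defect. If the broad event is intended, the definition sentence is wrong. If the narrow event is intended, the censoring sentence and the Appendix A entry are wrong, Section 6 is incomplete, and the SAP names no data field or attribution rule for it.

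**Conclusion.** The inconsistency is confirmed from the text and needs no assumption. The definition sentence of SAP 4.3.9.14 is narrower than its own censoring sentence, SAP Appendix A and the protocol; the difference is undeclared; and one type of subject is left with no status.

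The effect on the result is conditional. It requires that the narrow sentence is programmed and that at least one subject has new systemic therapy for non-GI aGVHD as first failure. FFS is then equal to or higher than under the protocol definition, never lower in the underlying curve. The size is zero with no such subject. Without censoring, it is 3.3 points of 30, or 6.7 points in an arm of 15, for each one who has no other failure by that time. How many there will be cannot be derived from the documents. The point should be corrected before the analysis is run, but it is not evidence that reported FFS will be biased.

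**What to change.** 1. In SAP 4.3.9.14, replace the GI-only phrase in the definition sentence with "addition of new systemic acute graft versus host disease (aGVHD) treatment". This agrees with the censoring sentence, the Appendix A FFS entry and the protocol.
2. State whether the Appendix A entry on additional systemic therapy also governs FFS. A bare pointer to Appendix A is not enough. That entry is labelled for complete and partial response, requires the eCRF confirmation of earlier progression, mixed response or non-response, and excludes added systemic steroids, whereas the protocol's FFS wording has none of these qualifiers. SAP 4.3.9.9 handles steroid increases differently again for duration of response, so the reader cannot assume a common rule.
3. If a GI-only FFS is wanted, keep it as a supportive analysis, declare it in Section 6, and say how therapy will be attributed to an organ, since the listed eCRF items do not record it.

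The cost is one or two SAP sentences, plus a Section 6 item if a GI-only version is kept. The broad event needs no new data. FFS may come out slightly lower than under the narrow wording if any such subjects exist.

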#### *4.3.9.15 Lower GI-aGVHD flare up to Day 182 up post-first dose of apraglutide*

The lower GI-aGVHD flare up to Day 182 rate is defined as the proportion of subjects experiencing a lower GI-aGVHD flare between the end of treatment due to CR and 182 days after the first dose of apraglutide. The denominator for the proportion is the number in the FAS. The number and percentage of subjects with lower GI-aGVHD flare up to Day 182 will be provided by apraglutide dose levels and in total along with the corresponding two-sided 95% confidence intervals using Clopper-Pearson exact method.

If 5 subjects or less experienced a lower Gi-aGVHD flare at the clinical cut-off date, the analysis of the lower GI-aGVHD flare data will be restricted to a listing of data related to flare.

*4.3.9.16 Graft Failure up to 2 years post-first dose of apaglutide*

Graft failure are collected in the AE form.

The graft failure time is defined as the time from the date of transplant to the date of the graft failure.

The graft failure will be summarized using Kaplan-Meier estimator. The number and percentage of subjects experiencing an event, and subjects censored will be summarized by apaglutide dose levels and in total. The median time-to-event will be presented where possible, along with the range and the associated two-sided 95% Brookmeyer-Crowley confidence interval. The event-free rate with 95% CI using Greenwood's formula will be provided for selected time points (e.g., 1, 3, 6, 12 and 24 months).

Plots of the Kaplan-Meier estimate for the graft failure will be presented by apaglutide dose levels and in total.

Subjects who are alive at the time of data cut-off and for which no graft failure event occurs will be right censored at their last follow-up visit.

Graft failure will be analyzed only for the EOT analysis.

*4.3.9.17 Infections and Sepsis from baseline to Day 91 and overall*

Infections and sepsis will be derived programmatically from AEs coded using MedDRA based on Sponsor-defined list (see Table 4-4).

The number and percentage of subjects experiencing infections and sepsis starting between the first dose of apaglutide up to Day 91 and until the end, as well as starting between the first dose of apaglutide up the end of the study, will be provided by apaglutide dose levels and in total.

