## 2.3 Sample Size Determination

The sample size calculation was fully reported in the protocol (section 7.8.1). It was planned to randomize 30 subjects to the 2 trial arms on a 1:1 ratio. It is calibrated such as five out of seven responders at the interim analysis enable a detection of an apaglutide signal at least 10% greater than the historical reference Day 56 durable overall response rate on the Lower GI MAGIC score with a probability of 88.2%.

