### 3.2 Secondary endpoints:

- Overall response rate at Day 56 on the lower GI tract MAGIC stage: defined as proportion of subjects with complete response (CR) or partial response (PR) on the lower GI tract MAGIC stage at Day 56.
- Overall response rate (PR and CR) at Days 14, 28, 91, 119, 147, and 182 on the lower GI tract MAGIC stage.
- Overall response rate (PR and CR) at Days 14, 28, 56, 91, 119, 147, and 182 by organ system (skin, lower and upper GI tract, and liver) on the total MAGIC grade.
- Proportion of all subjects who achieve a CR or PR at Day 28 and maintain a CR or PR at Day 56 [Only for Primary Analysis].
- Individual duration of lower GI response (according to the MAGIC score)
  - counted from the first response to return to baseline or worse
  - in subjects that were re-treated with apaglutide because of a lower GI-aGVHD flare, counted from the first response after apaglutide restart to return to baseline or worse
- Time to:
  - Partial lower GI-aGVHD response as defined by the MAGIC score
  - Complete lower GI-aGVHD response as defined by the MAGIC score
- Duration of response from Day 56 on the total MAGIC score: defined as the interval from the Day 56 response (PR and CR) to death or new systemic therapy for aGVHD (including an increase in steroids >2 mg/kg/day methylprednisolone (MP) equivalent), whichever occurs first, with at least 182 days of follow-up
- Duration of response from Day 28 on the total MAGIC: defined as the interval from the Day 28 response (PR and CR) to death or new systemic therapy for aGVHD (including an increase in steroids >2 mg/kg/day MP equivalent), whichever occurs first, with at least 182 days of follow-up
- Best overall response defined as overall response (PR or CR) at any time point up to and including Day 91 and before the start of additional systemic therapy for lower GI-aGVHD [Only for Primary Analysis]
- Failure-free survival up to 2 years post-first dose of apaglutide
- Incidence of malignancy relapse up to 2 years post-first dose of apaglutide [Only for EOT Analysis]
- Non-relapse mortality up to 2 years post-first dose of apaglutide

- Overall survival up to 2 years post-first dose of apaglutide [Only for EOT Analysis]
- Incidence of lower GI-aGVHD flare up to Day 182 after the first apaglutide dose following earlier cessation due to complete lower GI-aGVHD response
- Incidence of graft failure up to 2 years post-first dose of apaglutide [Only for EOT Analysis]

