## 4 STATISTICAL METHODOLOGY

### 4.1 General Considerations

Unless otherwise specified, continuous data will be summarized descriptively by apraglutide dose group (High Dose, Low Dose, Total Randomized, Low Body Weight, Total) and by time point. Descriptive statistics for continuous variables will include: the number of subjects, mean, standard deviation (sd), median, first and third quartiles (Q1, Q3), minimum, and maximum. All raw data will be presented to the original number of decimal places. Where appropriate, mean, median, and confidence interval will be presented to one more decimal, while standard deviation will be reported to two more decimals.

Unless otherwise specified, categorical data will be summarized descriptively by apraglutide dose group (High Dose, Low Dose, Total Randomized, Low Body Weight, Total) and time point. Summary statistics for categorical variables will contain counts and percentages. The numbers and percentages of missing data for a variable will be reported when applicable. Percentages will be reported to one decimal except for zero and one hundred percent, which will be presented as 0% and 100%, respectively; unless otherwise specified, the percentages are based on the number of subjects in the respective analysis set. Two-sided 95% confidence intervals for single proportion will be estimated via Clopper-Pearson exact method.

Analyses will be performed using SAS® (version 9.4 or higher, SAS Institute Inc., Cary NC.) and/or R (version 4.1.0 or higher, R Foundation for Statistical Computing, Vienna, Austria). When possible, note that the preferred use of methods: Hyndman and Fan's Definition 2 (1996) for quantiles estimation, "half away from zero" for rounding.

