## 4.2 Analysis Sets

### 4.2.1 Full Analysis Set

The Full Analysis Set (FAS) comprises all enrolled subjects (randomized and non-randomized). All efficacy estimations will be conducted using the FAS. All subjects will be analyzed according to the apraglutide planned dose (High Dose, Low Dose, Low Body Weight Dose) and in total (Total randomized, Total).

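### The flare rate counts only flares after stopping for complete response but divides by the whole FAS, so it understates recurrence after stopping and mixes it with the response rate

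*SAP*

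**What the plan says.** SAP 3.2 lists the incidence of lower GI-aGVHD flare up to Day 182 as a secondary endpoint and ties it to flare "following earlier cessation due to complete lower GI-aGVHD response". Protocol 1.5.2.2 carries the same condition.

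SAP 4.3.9.15 restricts the numerator to events occurring "between the end of treatment due to CR and 182 days after the first dose". It then fixes the base: "The denominator for the proportion is the number in the FAS". Under SAP 4.2.1 the FAS is everyone enrolled, randomized or not, whatever their response.

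The rate is to be given by dose level and in total with 95% Clopper-Pearson intervals. There is one exception: "If 5 subjects or less experienced a lower Gi-aGVHD flare at the clinical cut-off date", the analysis reduces to a listing. A rate is therefore tabulated only when at least 6 subjects have flared.

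The endpoint carries no restriction to the EOT analysis, so under SAP 1 it is analysed at both the Primary Analysis and the EOT analysis. SAP 6 does not mention the choice of denominator.

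**The concern.** Numerator and denominator describe different groups. A subject who never reached complete lower GI response, died first, stopped for another reason or stayed on treatment cannot contribute an event, but still counts as flare-free. The same holds for a subject whose treatment stopped with a partial response at Day 91. Protocol 2.2.2 allows such a subject to be re-treated for a flare, but that flare falls outside the endpoint.

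A reader will naturally take a flare rate after stopping for CR as the answer to how often disease comes back once the drug is withdrawn in a complete responder. The SAP's figure answers a different question, because it depends on the CR rate as well as on recurrence. A dose with no CRs would show 0% flares. Since the rate is displayed by dose, side-by-side reading can mislead.

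**Working it through.** The documents give no expected flare rate, no expected share stopping for CR and no sample size based on flare. There is no stated figure to reproduce, and all counts below are assumptions.

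**Inputs from the documents**
- Planned size: 30 randomized 1:1 (SAP 2.3), so 15 per dose, plus up to 4 low-body-weight subjects (SAP 2.1), so up to 34 in the FAS.
- Interval method: two-sided 95% Clopper-Pearson (SAP 4.1 and 4.3.9.15).
- Tabulation threshold: at least 6 subjects with a flare (SAP 4.3.9.15).

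**Identity**

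Let N be the FAS size, K the number stopping for CR and X the number of those who then flare. Then

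FAS rate = X/N = (K/N) × (X/K).

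The FAS rate equals the risk after stopping only if K = N.

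**Dilution**

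Assume a flare risk after stopping (X/K) of 30%:

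| Share stopping for CR (K/N) | FAS rate |
|---|---|
| 30% | 0.30 × 0.30 = 9% |
| 50% | 0.50 × 0.30 = 15% |
| 80% | 0.80 × 0.30 = 24% |

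The underlying recurrence risk is the same in every row.

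Example for the total, with X = 6, K = 14 and N = 34 (6 flares, so the table is produced):
- FAS: 6/34 = 17.6% (95% CI 6.8 to 34.5).
- Subjects who stopped for CR: 6/14 = 42.9% (17.7 to 71.1).
- Check: 14/34 × 6/14 = 6/34.

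**Dose order**

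Suppose the flare risk is higher at low dose. The FAS rate is then higher at high dose whenever (high/low ratio of shares stopping for CR) > (low/high ratio of flare risks).

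Example with 3 + 4 = 7 flares, so the table is produced:

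| | Stopped for CR | Flares | FAS rate (95% CI) | Rate among those who stopped for CR (95% CI) |
|---|---|---|---|---|
| Low dose | 6/15 | 3 | 3/15 = 20.0% (4.3 to 48.1) | 3/6 = 50.0% (11.8 to 88.2) |
| High dose | 12/15 | 4 | 4/15 = 26.7% (7.8 to 55.1) | 4/12 = 33.3% (9.9 to 65.1) |
| Total randomized | 18/30 | 7 | 7/30 = 23.3% (9.9 to 42.3) | 7/18 = 38.9% (17.3 to 64.3) |

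Here the ratio of shares is 0.80/0.40 = 2.0 and the ratio of risks is 0.50/0.333 = 1.5, so the order reverses. All the intervals overlap widely.

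**How often the two bases disagree**

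This was simulated with 15 subjects per dose and 400,000 trials per scenario, keeping trials with at least 6 flares.
- With true shares of 40% and 80% (low, high) and true risks of 50% and 33.3%, the two denominators rank the doses oppositely in about 34% of those trials.
- With equal shares of 50% and risks of 50% and 35%, they do so in about 8%.

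**Time at risk**

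The window closes at Day 182 from first dose, so follow-up after stopping depends on when the subject stopped:
- Week 8 (Day 56): 182 − 56 = 126 days.
- Week 13 (Day 91): 182 − 91 = 91 days.
- During optional treatment: fewer still.

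The Primary Analysis is triggered once all subjects have reached Day 91 or withdrawn (SAP 1). Some may not have reached Day 182, and SAP 4.3.9.15 has no rule for incomplete follow-up.

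**The case against.** The strongest defence is that the denominator is deliberate, disclosed and consistent with the protocol. Protocol 7.5.1 places all efficacy evaluations on the FAS, and SAP 4.1 bases percentages on the analysis set unless stated otherwise. The endpoint is an incidence timed from first dose, and the proportion of all enrolled subjects who stopped for CR and then flared is a legitimate quantity. This stands: the figure is not invalid. It does not, however, show recurrence among those who stopped, and nothing in 4.3.9.15 warns the reader of that.

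A second defence is that little rests on the dose ranking. SAP 6, item 12, removes the dose-effect endpoint because no formal comparison will be made, and with 5 or fewer flares no rate appears at all. This also stands and limits the consequence. The understatement in the total column needs no dose comparison.

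A third is that related information is already planned. Lower GI CR counts are given by visit, and SAP 4.3.9.7 analyses duration of lower GI response in responders only. That analysis starts at first response, not at cessation, so it does not supply the missing rate.

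Finally, stopping for CR is a post-randomization outcome, so a contrast among those who stopped compares selected subgroups. This is correct, and the conditional rate should not be read as a causal dose effect.

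A reader might infer more: that the FAS rate automatically favours the less effective dose, or will rank the doses wrongly. The documents do not support that. A lower CR share gives a lower FAS rate only if flare risk is not correspondingly higher, and no CR-stop or flare rates are given from which a reversal could be predicted.

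**Conclusion.** The point holds in limited form. By construction, the SAP's flare rate is the share stopping for CR times the flare risk after stopping, and it understates that risk whenever some FAS subjects do not stop for CR and flares occur. In the assumed example for the total, the gap is 18% against 43%. Reversal of the dose order is possible, not certain; it requires the shares stopping for CR to differ enough between doses. The identity follows from the SAP's definitions alone, whereas every numerical size rests on assumed counts. Because the endpoint is secondary and descriptive and the FAS figure is a valid unconditional incidence, this is an inexpensive improvement to reporting rather than a flaw that threatens the trial's conclusions. It also fits the SAP's own practice: the duration-of-response analyses in 4.3.9.7 and 4.3.9.9 are restricted to responders.

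**What to change.** Amend SAP 4.3.9.15 as follows.

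1. Use as denominator the subjects who stopped apraglutide because of complete lower GI response by Day 182. Report n/N with the Clopper-Pearson interval by dose and in total, so that the number at risk is visible.
2. Keep the FAS percentage as a supplementary line, labelled as the proportion of all enrolled subjects who stopped for CR and then flared.
3. Add cumulative incidence of flare from the cessation date, with death as a competing event and censoring at last follow-up or Day 182. This handles unequal time at risk and incomplete follow-up at the Primary Analysis, which a crude proportion does not.
4. State that the dose contrast is descriptive, because the denominator is defined after randomization.

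The first two changes need only a sentence or two and no new data collection; the third is one further analysis. The price is smaller denominators and wider intervals, for example 18 to 71 instead of 7 to 35 percent in the illustration for the total.
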